7.2.3 SPECIMEN PREPARATION, HANDLING, AND STORAGE

Refer to the Laboratory Manual for Medpace Central Laboratories.

7.2.4 SPECIMEN SHIPMENT

Refer to the Laboratory Manual for Medpace Central Laboratories.

7.3 STUDY SCHEDULE

7.3.1 PRESCREENING

Prior to entry into a Samumed study for OA of the knee, subjects must have a radiograph taken and read by the Sponsor-specified central reader. This radiograph may qualify the subject for one or more Samumed studies.

Prior to the Screening Visit, the subject's prescreen radiograph report must be reviewed to confirm eligibility for this study.

7.3.2 SCREENING

Screening Visit

The Screening Visit must occur within 7 to 11 days prior to Day 1.

The Investigator or designee must explain the nature of the study protocol and associated risks to the potential study participant. The potential participant must be allowed to review the study information and to ask questions before being asked to sign and date the ICF. Written informed consent must be provided, signed, and dated by the potential study participant prior to initiation of any screening evaluations or other study-related procedures. The signature, date, and the name of the individual at the site who obtained the informed consent will be recorded. After written informed consent is obtained, the subject will be assigned a subject number.

Investigators will maintain a confidential log of all subjects who have been screened for participation in the study whether or not the subject was eligible for study participation.

The following procedures and assessments will be performed initially during the Screening Visit:

- Physical examination, including knee examination of both knees and confirmation of target knee
- Review of prescreen radiograph report for target knee
- Documentation of demographic information, including date of birth, sex, race, and ethnicity
- Subject NSAID training
- Documentation of current and past medical history including prior procedures and non-drug therapies, assistive device usage, documentation of current medications, and review of prior medication excluded by the protocol
- Documentation of past treatments for knee OA
- WPI&SS assessment
- Height and weight measurements
- Vital sign measurements (pulse rate, blood pressure, respiratory rate, and temperature)

It is recommended that the results from these evaluations will be compared with inclusion/exclusion criteria to determine subject eligibility. If the subject is confirmed eligible, the following procedures and assessments will be performed:

- Pregnancy test (serum-based) for WOCBP
- Urine drug test
- Venipuncture and collection of samples for clinical laboratory tests
- Electronic diary device provision and subject training for electronic diary and questionnaire completion on the electronic device
- Training on accurate pain reporting and placebo response reduction

Starting on the day of the Screening Visit, after the site visit, subjects will begin completion of daily pain NRS assessments remotely on their electronic devices in the evening (between 5:00 pm and 11:59 pm).

Note: Five days after the Screening Visit (or up until the day before the Day 1 visit), subjects will complete the WOMAC and Patient Global Assessment, in addition to the pain NRS assessment, in the evening (between 5:00 pm and 11:59 pm) remotely on their electronic devices. Refer to [Section 7.3.8](#) for a schedule of electronic diary and questionnaire completion.

7.3.3 RANDOMIZATION

Day 1

This visit must occur within 7 to 11 days of the Screening Visit.

The following procedures and assessments will be performed at Day 1 prior to randomization:

- Review of current and past medical history, documentation of current medications, and review of prior medication excluded by the protocol
- WPI&SS assessment
- Review of pain NRS electronic diary compliance from the Screening Visit to Day 1
- Electronic questionnaire review (WOMAC and Patient Global Assessment)
- Assessment of NSAID/acetaminophen pain medication usage to establish/document baseline usage
- Physical examination, including knee examination of both knees
- Vital sign measurements (pulse rate, blood pressure, respiratory rate, and temperature)
- Pregnancy test (urine-based) for WOCBP

Results from the Screening Visit and Day 1 evaluations will be compared with inclusion/exclusion criteria to determine subject eligibility.

The following procedures and assessments will be performed at Day 1 following randomization:

- IA injection of randomized study medication by the Unblinded Investigator (injector)
- Collection of AE and concomitant procedures/medication data

Note: After the Day 1 site visit, subjects will complete the following in the evening (between 5:00 pm and 11:59 pm) remotely on their electronic devices:

- Daily pain NRS assessments
- WOMAC and Patient Global Assessment questionnaires at Week 4 (with a window of \pm 3 days) and Weeks 12, 24, and 28 (with windows of \pm 7 days)

Refer to [Section 7.3.8](#) for a schedule of electronic diary and questionnaire completion.

7.3.4 FOLLOW-UP

Week 4

The Week 4 visit should occur on Day 29 (with a window of \pm 3 days).

The following procedures and assessments will be performed at these visits:

- Collection of AE and concomitant procedures/therapies/medication data
- Assessment of NSAID/acetaminophen usage
- Review of pain NRS, WOMAC, and Patient Global Assessment electronic diary compliance
- Physical examination, including knee examination of both knees
- Vital sign measurements (pulse rate, blood pressure, respiratory rate, and temperature)
- Venipuncture and collection of samples for clinical laboratory tests

Weeks 8, 16, and 20 (Phone Visits)

Sites will contact subjects for phone visits on Days 57, 113, and 141 (with windows of \pm 7 days). The following assessments will be performed at each visit:

- Collection of AE and concomitant procedures/therapies/medication data
- Assessment of NSAID/acetaminophen usage

Weeks 12 and 24

The Week 12 visit should occur on Day 85 (with a window of \pm 7 days) and the Week 24 visit should occur on Day 169 (with a window of \pm 7 days).

The following procedures and assessments will be performed at these visits:

- Collection of AE and concomitant procedures/therapies/medication data
- Assessment of NSAID/acetaminophen usage
- Review of pain NRS, WOMAC, and Patient Global Assessment electronic diary compliance
- Physical examination, including knee examination of both knees
- Vital sign measurements (pulse rate, blood pressure, respiratory rate, and temperature)
- Venipuncture and collection of samples for clinical laboratory tests

7.3.5 FINAL STUDY VISIT

Week 28 End of Study

This final study visit should occur on Day 197 with a window of \pm 7 days.

The following procedures and assessments will be performed at Week 28 (EOS):

- Collection of AE and concomitant procedures/therapies/medication data
- Review of medical history
- Assessment of NSAID/acetaminophen usage
- Physical examination, including knee examination of both knees
- Weight measurement
- Vital sign measurements (pulse rate, blood pressure, respiratory rate, and temperature)
- Venipuncture and collection of samples for clinical laboratory tests

7.3.6 EARLY TERMINATION VISIT

If possible, the following procedures and assessments should be performed within 14 days of subject premature withdrawal or termination.

- Collection of AE and concomitant procedures/therapies/medication data

Protocol SM04690-OA-10

Samumed, LLC

AM03V00

12 May 2020

- Review of medical history
- Assessment of NSAID/acetaminophen usage
- Physical examination, including knee examination of both knees
- Weight measurement
- Vital sign measurements (pulse rate, blood pressure, respiratory rate, and temperature)
- Venipuncture and collection of samples for clinical laboratory tests

7.3.7 SCHEDULE OF EVENTS TABLE

Procedure	Screening Visit ^a (Days -11 to -7)	Day 1 ^b	Week 4 (Day 29 ±3 days)	Weeks 8, 16, 20 ^c (±7 days) (Phone Visits)	Week 12 (Day 85 ±7 days)	Week 24 (Day 169 ±7 days)	Week 28 (EOS) (Day 197 ±7 days) / ET
Informed consent	X						
Inclusion & exclusion criteria	X	X					
Demographics	X						
Medical history	X	X					X ^d
Current and prior procedures/medications	X	X					
Past treatments for knee OA pain	X						
Subject NSAID training	X						
Investigator assessment of NSAID/ Acetaminophen usage		X	X	X	X	X	X
Serum pregnancy test ^e	X						
Urine pregnancy test ^e		X					
Urine drug test	X						
WPI&SS	X	X					
Review prescreen radiograph report	X						
Physical examination	X	X	X		X	X	X
Knee examination	X	X	X		X	X	X
Selection of target knee	X						
Height	X						
Weight	X						X
Vital signs	X	X	X		X	X	X
Clinical laboratory sampling	X		X		X	X	X
Electronic diary provision and questionnaire training	X ^f						
Review Pain NRS compliance		X ^g	X		X	X	
Review WOMAC compliance		X ^h	X		X	X	
Review Patient Global Assessment compliance		X	X		X	X	
Randomization		X					
Intra-articular injection		X					
AEs and concomitant procedures/medications		X	X	X	X	X	X

Protocol SM04690-OA-10

Samumed, LLC

AM03V00

12 May 2020

- ^a The screening period is a minimum of 7 days and a maximum of 11 days. The Screening Visit should only occur after review of the prescreen radiograph report for eligibility in this study.
- ^b At Day 1, all procedures should be performed prior to study medication injection except for collection of AE and concomitant procedures/medication data.
- ^c Phone visits should take place on Days 57, 113, and 141 (\pm 7 days for all visits).
- ^d Review medical history to capture End Date(s), if applicable, of any ongoing medical history(ies) collected at the Screening Visit and Day 1.
- ^e Serum and urine pregnancy tests are to be performed on WOCBP only.
- ^f Electronic diary devices will be provided to subjects at the Screening Visit; subject electronic diary and questionnaire training including accurate pain reporting and placebo response reduction training will be conducted at the Screening Visit. Accurate pain reporting and placebo response reduction training is recommended at Day 1 and Weeks 4, 12, and 24.
- ^g Electronic diary compliance and assessment of target and non-target knee pain scores for daily pain NRS over the screening period will be reviewed at Day 1 prior to randomization to determine subject eligibility.
- ^h WOMAC questionnaire will be reviewed at Day 1 prior to randomization to determine subject eligibility.

7.3.8 SCHEDULE OF ELECTRONIC DIARY AND QUESTIONNAIRE COMPLETION TABLE

	WOMAC and Patient Global Assessment	Daily pain NRS
Study Week/Day	WOMAC and Patient Global Assessment will be completed by subjects 5 days after the Screening Visit (or up until the day before the Day 1 visit), at Week 4 (with a window of \pm 3 days), and at Weeks 12, 24, and 28 (with a window of \pm 7 days) in the evening (between 5:00 pm and 11:59 pm local time) remotely on their electronic devices, as outlined below; ranges shown are inclusive.	Pain NRS should be completed daily starting after the Screening Visit. Subjects will complete the diary in the evening (between 5:00 pm and 11:59 pm local time) remotely on their electronic devices. Diary completion should occur every day including on study visit days.
Screening Visit		
5 days after the Screening	Baseline WOMAC and Patient Global Assessment questionnaires (or up until the day before the Day 1 visit)	Complete daily starting on the same day of the Screening Visit (after the visit); pain NRS assessments are to be completed for each knee.
Day 1	N/A	
Week 4 (Day 29)	Complete between Day 26 and 32	Starting on the same day of Day 1 (after the visit), pain NRS assessments are to be completed for the target knee only. Complete daily.
Week 12 (Day 85)	Complete between Day 78 and 92	
Week 24 (Day 169)	Complete between Day 162 and 176	
Week 28 (Day 197)	Complete between Day 190 and 204	

7.4 JUSTIFICATION FOR SENSITIVE PROCEDURES

Not applicable for this study.

7.5 CONCOMITANT MEDICATIONS, TREATMENTS, AND PROCEDURES

Details regarding the name, indication, route of administration, dose, and frequency of all medications taken within 30 days prior to the Screening Visit through Week 28 (EOS)/ET will be recorded in the “Prior and Concomitant Medications” eCRF. “All medications” should include prescription, over-the-counter, supplements, as well as herbal or alternative medications.

Procedures or non-drug therapies that are ongoing, new, or modified at or after the Screening Visits must be recorded on the “Procedures and Non-Drug Therapies” eCRF.

AE assessments should include consideration of any new or modified concomitant therapies administered to the subject.

7.5.1 PRECAUTIONARY MEDICATIONS, TREATMENTS, AND PROCEDURES

Not applicable to this study.

7.6 PROHIBITED MEDICATIONS, TREATMENTS, AND PROCEDURESProhibited Concomitant Medications and Procedures:

- Any IA injection, including glucocorticoids, hyaluronic acid derivatives, PRP, stem cell therapies, or other agents with therapeutic intent, into either knee is prohibited while the subject is on study; IA injection of glucocorticoids, hyaluronic acid derivatives, PRP, stem cells, or other therapeutic agents into joints other than the knee is allowed.
- The following medications are prohibited while the subject is on study:
 - Opioids; short-term use of opioids as part of anesthesia or procedural sedation during the study period is permitted
 - Centrally acting analgesics (e.g., duloxetine) (refer to [Appendix 2](#))
 - Topical local anesthetic agents; short-term use as part of anesthesia, including for study injections during the study period is permitted
 - Other anticonvulsants not listed in [Appendix 2](#)
 - Systemic glucocorticoids ≥ 10 mg of prednisone per day or the equivalent; epidural, inhaled, intranasal, and topical glucocorticoids are permitted
 - Drugs screened to assess eligibility, unless clinically indicated and allowed by the protocol: amphetamine, buprenorphine, cocaine, methadone, opiates, PCP, propoxyphene, barbiturates, benzodiazepine, methaqualone, and tricyclic antidepressants
 - Electrotherapy (refer to [Appendix 2](#)), acupuncture, formalized physical therapy (i.e., prescribed by a medical professional), therapeutic ultrasound, and/or chiropractic treatments for knee OA are prohibited while the subject is on study.

- Elective surgery, including arthroscopy, is prohibited while the subject is on the study. Non-surgical invasive procedures conducted for a diagnostic or therapeutic purpose that are scheduled during the study period are not prohibited. Examples include, but are not limited to endoscopy, colonoscopy, bronchoscopy, cystoscopy, radiologic procedures such as coronary artery catheterization with or without intervention, and non-surgical cosmetic procedures such as Botox or other cosmetic injections.
- Subjects are prohibited from participating in any other clinical research trial that includes the receipt of an IP or any experimental therapeutic procedure. Subjects are also prohibited from participating in any observational research trial while on study.

The Investigator should notify the Samumed Medical Monitor immediately if any prohibited therapies are required to ensure subject safety.

7.7 PROPHYLACTIC MEDICATIONS, TREATMENTS, AND PROCEDURES

Not applicable to this study.

7.8 RESCUE MEDICATIONS, TREATMENTS, AND PROCEDURES

Subjects are allowed to remain on their stable regimen of NSAIDs/acetaminophen during this study and may change their usage as needed for pain management, including for the rescue of knee pain.

7.9 PARTICIPANT ACCESS TO STUDY AGENT AT STUDY CLOSURE

Not applicable to this study.

8. ASSESSMENT OF SAFETY

8.1 SPECIFICATION OF SAFETY PARAMETERS

Safety assessments include physical examinations, vital signs, clinical laboratory tests, collection of AEs and SAEs, concomitant medications, and general medical evaluations.

8.1.1 DEFINITION OF ADVERSE EVENTS (AE)

AEs in the eCRF will be classified according to the most recent US FDA definitions and in a manner consistent with ICH-GCP guidelines. As such the following definitions will be used:

An AE is any unfavorable and unintended sign, symptom, or disease temporally associated with the use of an IP or other protocol-imposed intervention, regardless of attribution. An AE may include intercurrent illnesses or injuries that represent an exacerbation (increase in frequency, severity, or specificity) of preexisting conditions (e.g., worsening of asthma).

Whenever possible, it is preferable to record a diagnosis as the AE term rather than a series of symptoms relating to a diagnosis. Fluctuations of pre-existing conditions, including the disease under study that does not represent a clinically significant exacerbation or worsening, need not be considered AEs. In order to classify AEs and diseases, preferred terms will be assigned by the

Sponsor to the original terms entered on the eCRF, using the Medical Dictionary for Regulatory Activities (MedDRA).

In this protocol, signs and symptoms of exacerbation or worsening of target knee OA will be captured in the context of efficacy assessments and recorded on specific pages of the eCRF or electronic diary. Anticipated fluctuations or anticipated deterioration (in the opinion of the Investigator) of the underlying disease (target knee OA) will not be considered as AEs nor captured on the AE page of the eCRF.

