7. STUDY PROCEDURES AND SCHEDULE

7.1 STUDY PROCEDURES/EVALUATIONS

7.1.1 STUDY SPECIFIC PROCEDURES

Collection of Adverse Events Data

Data regarding AEs will be collected in this study. AEs are events that occur during the study that are not present prior to Day 1 study medication injection, or, if present at the time of study medication injection, have worsened in severity during the study. AEs will be assessed at each in-person and phone visit from the time of study medication injection on Day 1 through Week 28 (EOS)/ET.

Each subject will be observed and queried by the Investigator or designee at each study visit for any continuing AEs or new AEs since the previous visit. The subject may be asked to return to the site for an unscheduled visit if an AE occurs between study visits, and if, in the opinion of the

Investigator, the AE requires a study visit for full evaluation. The following information will be recorded within the eCRF for each AE: Description of the event, date of onset and resolution, etiology, and severity as assessed by the Investigator according to the Clinical Data Interchange Standards Consortium (CDISC) Severity/Intensity Scale for Adverse Events (AESEV) ([Table 1](#)), causal relationship to study medication, outcome, and any action taken.

In this protocol, signs and symptoms of exacerbation or worsening of target knee OA will be captured in the context of efficacy assessments and recorded on specific pages of the eCRF or electronic diary. Anticipated fluctuations or anticipated deterioration (in the opinion of the Investigator) of the underlying disease (target knee OA) will not be considered as AEs nor captured on the AE page of the eCRF.

Whenever possible, it is preferable to record a diagnosis as the AE term rather than a series of symptoms relating to a diagnosis. Fluctuations of pre-existing conditions that do not represent a clinically significant exacerbation or worsening need not be considered AEs.

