A knee examination of both knees will be conducted at the Screening Visit, Day 1, and at Weeks 4, 12, 24, and 28 (EOS)/ET. Results of the knee examination will be noted in the source documents. Any clinically significant finding noted prior to study medication injection should be recorded as medical history. If it is found after study medication injection, it should be reported as an AE.

Presence of unilateral or bilateral symptomatic knee OA will be recorded in the eCRF at the Screening Visit. If the subject has OA in both knees, the site is to establish the target knee as the knee with greater pain at the Screening Visit based on the subject's evaluation and the Investigator's clinical judgment. If the Investigator's clinical judgement of the target knee differs from the subject-reported target knee (as reported during prescreen), sites should contact the Sponsor for further guidance.

Vital Signs

Vital signs will be measured by a qualified staff member at the Screening Visit, Day 1, and Weeks 4, 12, 24, and 28 (EOS)/ET.

At each time point, the following vital signs will be measured:

- Body temperature
- Pulse rate
- Respiratory rate
- Blood pressure (systolic and diastolic) after the subject rests (sitting or supine) for at least 5 minutes

Any measurement that is, in the opinion of the Investigator, abnormal AND clinically significant must be recorded as medical history if found prior to study medication injection or as an AE if found after study medication injection.

Height and Weight

Height measurements will be taken at the Screening Visit only. Weight measurements will be taken at the Screening Visit and Week 28 (EOS)/ET.

Review of Prescreen Radiograph Report

Prior to entry into a Samumed study for OA of the knee, subjects must have a radiograph taken and read by the Sponsor-specified central reader. Prior to the Screening Visit, the subject's prescreen radiograph report must be reviewed to confirm eligibility for this study. At the Screening Visit, after confirmation of the target knee by the Investigator, the subject's prescreen radiograph report must be reviewed for the target knee to confirm compliance with inclusion/exclusion criteria.

Widespread Pain Index and Symptom Severity (WPI&SS) Form

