9.4 Other Efficacy Analysis

Change over time in WOMAC Pain and WOMAC Total scores will be characterized using a MMRM to estimate change from baseline with treatment group, week, treatment \times week interaction and baseline value as covariates. The model will include all timepoints, but will be evaluated at Weeks 12, and 24. Unadjusted 95% confidence intervals and P values will be reported.

The number and percent of subjects reporting Patient Acceptable Symptom State (PASS), 30% improvement, 50% improvement, and 70% improvement in Pain NRS, WOMAC Function, and

Patient Global Assessment will be summarized. PASS is defined as a reported value of less than or equal to 30 on a 0-100 scale. Logistic regression analysis will be implemented for improvement in these assessments as well, with 95% confidence intervals and P values reported.

The analyses described above will be performed on subjects in the FAS.

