10.1 Adverse Events

All AEs collected in this study are treatment emergent events that occur during the course of the study that are not present prior to Day 1 study medication injection, or, if present at the time of study medication injection, have worsened in severity during the course of the study. AEs will be presented in summary tables depicting the number and percent of unique subjects experiencing each AE and the number of AEs overall and within each treatment group. The following summaries will be provided:

- All AEs and all SAEs by severity and relationship to study product
- AEs by highest degree of seriousness, severity, and relationship to study drug
- AEs by MedDRA system organ class and preferred term
- AEs with incidence of greater than 2% in the active treatment group sorted by preferred term incidence
- Target-knee-related AEs and SAEs sorted by preferred term incidence
- AEs leading to study withdrawal
- SAEs in subjects diagnosed with COVID-19

Separate subject-level listings will be provided for all AEs and all SAEs.

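### Anticipated target-knee worsening is kept off the AE page because efficacy data capture it, but the SAP never counts subjects who worsened

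*Protocol*

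**What the plan says.** **What stays off the AE page.** Protocol 8.1.1 states that "signs and symptoms of exacerbation or worsening of target knee OA will be captured in the context of efficacy assessments". The next sentence has as its subject "Anticipated fluctuations or anticipated deterioration (in the opinion of the Investigator) of the underlying disease (target knee OA" and rules that these "will not be considered as AEs nor captured on the AE page of the eCRF". Protocol 7.1.1 (Collection of Adverse Events Data) has the same text, and SAP 7.4.1 repeats the exclusion. The Amendment 01 table in Protocol Appendix 3 gives the reason: knee pain is an endpoint, so efficacy measures will record it.

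**What points the other way.**
- Protocol 8.1.1 also says that fluctuations of pre-existing conditions, "including the disease under study that does not represent a clinically significant exacerbation or worsening, need not be considered AEs". This exempts only changes short of clinically significant worsening.
- Protocol 7.1.1 (Collection of Adverse Events Data) counts as AEs conditions that, "if present at the time of study medication injection, have worsened in severity during the study".
- Protocol 7.1.1 (Knee Examination) says of a clinically significant finding: "If it is found after study medication injection, it should be reported as an AE".

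**What the SAP reports.**
- SAP 10.1 plans a table of "Target-knee-related AEs and SAEs sorted by preferred term incidence".
- SAP 9.2.1 fits an MMRM for mean change, evaluated at Week 12.
- SAP 7.1 summarises change by visit with mean, SD, median, minimum and maximum.
- SAP 9.4 counts subjects reaching PASS and "30% improvement, 50% improvement, and 70% improvement in Pain NRS", WOMAC Function and Patient Global Assessment.
- SAP 12.3 describes change in Total NSAID Score by 4-week period. It puts the Investigator's assessment of NSAID/acetaminophen usage in a listing only.

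**The concern.** The exclusion is defensible if the efficacy data are then used to show worsening. They are not used in that way. Every planned subject-level category looks at improvement, and a mean combines the few who flare with the many who improve.

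The injected joint is where local harm from an intra-articular product would be expected, and Protocol 2.3.1 names local site reactions as an injection risk. The word "anticipated" has no criteria and would be applied at about 100 centers. A flare put down to OA would therefore drop out of the target-knee AE table, and no other table would count it by arm. What is at stake is the completeness of the local safety report. The primary efficacy result is not affected.

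**Working it through.** **1. Can each planned output show how many subjects worsened?**

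| Output | Counts worsened subjects by arm? |
|---|---|
| Target-knee AE table (SAP 10.1) | Only events that reached the AE page |
| MMRM (SAP 9.2.1, 9.3.1) | No, means only |
| Descriptive change (SAP 7.1) | No; the maximum shows the single worst subject |
| PASS and 30/50/70% (SAP 9.4) | No, improvement only |
| Total NSAID Score (SAP 12.3) | No; a distribution summary, not tied to target-knee pain |
| Investigator's NSAID assessment (SAP 12.3) | No, listing only |
| Events of special interest (Protocol 8.4.4) | Not applicable to this study |

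**2. Timing.** After Day 1 the first scheduled knee examination and AE query is Week 4, Day 29 ± 3 (Protocol 7.3.4, 7.3.7). An earlier flare depends on the subject reporting it or on an unscheduled visit. The diary runs daily from Day 1 (Protocol 7.3.8).

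**3. Sensitivity of the mean.** Inputs from SAP 5, re-estimated: follow-up SD 2.4, correlation 0.25, 225 per arm. Original inputs: SD 3.0, 325 per arm.

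SE of the difference = SD × √(1 − 0.25²) × √(2/n)
- 2.4 × 0.968 × √(2/225) = 0.219
- 3.0 × 0.968 × √(2/325) = 0.228

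As a check, these SEs with a difference of 0.8 and two-sided 5% give power of 95.5% and 94.0% for Pain NRS. The documents state 94.3% and 93.5% from simulation.

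The flare rates and sizes are assumptions, because the documents give none. If 3% to 10% of the active arm is 2 to 3 points higher, the mean shifts by 0.03 × 2 = 0.06 up to 0.10 × 3 = 0.30. With no other drug effect, the mean comparison detects this with about 5% to 28% power.

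**4. Sensitivity of a count of weekly averages.** Baseline SD 1.2 and follow-up SD 2.4 give an SD of change of √(1.44 + 5.76 − 2 × 0.25 × 1.2 × 2.4) = 2.4. The placebo mean change is 3.8 − 6.0 = −2.2. Assume normal change, both arms at −2.2, and a flare that adds 3 points in 7% of active and 2% of placebo subjects.

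| Rise from baseline | Without flare | With flare | Placebo | Active | Difference / SE |
|---|---|---|---|---|---|
| ≥ 1 | 9.1% | 46.7% | 9.9% | 11.7% | 0.64 |
| ≥ 2 | 4.0% | 30.9% | 4.5% | 5.9% | 0.64 |
| ≥ 3 | 1.5% | 18.0% | 1.8% | 2.7% | 0.59 |

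For the ≥ 1 row, active = 0.07 × 0.467 + 0.93 × 0.091 = 0.117. The SE is √[(0.117 × 0.883 + 0.099 × 0.901)/225] = 0.029.

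If the active arm also has the planned benefit (3.0 − 6.0 = −3.0), the active percentages become 6.8, 3.2 and 1.3. All three are below placebo.

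**5. Dilution by weekly averaging.** Two days at +3 raise a weekly average by 2 × 3/7 = 0.86. Two days at +5 raise it by 1.43. A rise of 2 points or more would miss both, while the daily scores would show them. The documents give no daily variance, so the gain from daily scores cannot be calculated.

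**The case against.** **The exclusion is narrow.** It covers only anticipated OA change. A reader might infer that all target-knee worsening is kept off the AE page, or that injection reactions go unreported. The documents do not support that. AEs are defined regardless of attribution and queried at every clinic and phone visit. Clinically significant knee findings after injection are AEs, and target-knee AEs have their own table. This stands, and it limits the point to flares classed as anticipated OA.

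**The AE passages can be read together.** Protocol 7.1.1 gives both the general rule and the exception, so a site could record what is unanticipated or clinically significant. That is a fair reading. The text still does not say what to do with a change that is both anticipated and clinically significant.

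**Worsening is not wholly unreported.** Minimum and maximum change, Total NSAID Score by 4-week period, AEs leading to withdrawal and discontinuation reasons by arm are all planned. This also stands, but none of them counts subjects who worsened.

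**A count may be no more sensitive than the mean.** A reader might set an assumed 7% against 2% as 0.05 × 3 = 0.15 points, or 0.15/0.219 = 0.7 SE, on the mean. The same excess as a proportion is 0.05/0.0194 = 2.6 SE, which would make the table look far more powerful. That contrast fails. It treats 3 points as a shift from the expected score for the mean and as a rise from baseline for the count, and it ignores background worsening. Used consistently as a shift, the count gives about 0.6 SE. Used consistently as a rise from baseline, the mean shift is 0.05 × 5.2 = 0.26 to 0.05 × 6.0 = 0.30, or 1.2 to 1.4 SE. This objection stands in full.

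**Conduct is over.** The SAP was signed in October 2021 and already lists the 26 subjects excluded from the PPAS. New AE wording cannot recover events that were never recorded. This stands for the wording but not for the table, which uses diary data already held.

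**Conclusion.** The concern holds in a limited form. The plan keeps anticipated target-knee worsening off the AE page on the ground that efficacy data capture it, and then includes no analysis that counts it. This follows from the text and needs no assumption. The gap covers flares that an Investigator classes as anticipated OA, and matters most before Week 4, when no knee examination is scheduled.

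The numerical consequence is uncertain because no flare rate is documented. Under the assumed range the mean comparison has about 5% to 28% power to show a flare. The case for the table does not rest on superior power. On the SAP's follow-up inputs, a count of weekly averages is about as sensitive as the mean, and an average benefit could reverse its direction. Those inputs describe follow-up; no means are given for Weeks 1 to 4. The case is that a safety outcome moved out of the AE data should be reported somewhere by arm. The documents do not show that a flare occurred or that one was concealed.

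**What to change.** **Add one descriptive table by arm on the Safety Analysis Set.** Give the number and percent of subjects whose target-knee Pain NRS rose from baseline by a prespecified amount:
- in a prespecified early post-injection window, using daily scores as well as weekly averages;
- over the whole study, using weekly averages.

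The amount and the window should be fixed before unblinding. If unblinding has already happened, label the table as added afterwards. No test is needed, and neither alpha nor the primary analysis is touched.

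**Reconcile the AE passages.** Protocol 7.1.1 (Collection of Adverse Events Data and Knee Examination), Protocol 8.1.1 and SAP 7.4.1 should agree on when target-knee worsening is an AE. The SAP or study report should state which rule was applied, so that the target-knee AE table can be read correctly.

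**Cost.** One extra table from existing data and a few sentences. The table should carry a note that its sensitivity is modest and that similar percentages in the two arms would not exclude a short flare.
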